8.3. Sample Size Determination

The study will enroll approximately 390 subjects. In two Phase 3 clinical trials with adalimumab (PIONEER I and II; [Kimball et al, 2016a](#)), the proportions of subjects in the placebo control group achieving a HiSCR at Week 12 were 26.0% and 27.6%, respectively. Hence, if the control group only receives placebo, one may assume a HiSCR at Week 12 of approximately 30%. The average HiSCR at Week 12 in the adalimumab groups in PIONEER I and II were 41.8% and 58.9%, respectively with an average of approximately 50% ([Kimball et al, 2016a](#)). The attrition rate throughout the trial is estimated to be approximately 7%. A sample size of approximately 130 subjects per treatment group (390 in total) at a Type I error rate of $\alpha = 0.05$ (two-sided) provides approximately 90% power to detect a 20% superiority of avacopan compared to the placebo control group in HiSCR at Week 12, assuming an HiSCR at Week 12 of 50% in the avacopan group.

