8.8. Statistical Analysis Methodology

8.8.1. General Approach

All study data will be summarized by treatment using descriptive statistics. Categorical variables will be reported as frequency and percent (e.g., gender, race). Continuous variables will be reported as number of subjects, mean, standard deviation, median, minimum, and maximum (e.g., age, weight). All summaries, statistical analyses, and individual subject data listings described below will be completed using Version 9.3 or later of the SAS Statistical Analysis System (SAS Institute, Inc. Cary, NC).

All statistical testing will be two-sided, with the Type I error rate at $\alpha = 0.05$.

Baseline is defined as the last value prior to start of dosing with study drug (typically the Day 1 pre-dose value).

Non-Responder Analysis: For non-responder analysis, the following imputation rules will be applied to categorical and continuous efficacy variables, respectively:

- Categorical Efficacy Variables: Non-Responder Imputation (NRI) will be used as the primary analysis. Last Observation Carried Forward (LOCF) will be the secondary approach for the non-responder analysis.
- Continuous Efficacy Variables: LOCF will be used as the primary analysis. The valid assessments from last visit prior to the visit the subject was considered a non-responder will be carried forward to the end of study for continuous efficacy variables. Baseline efficacy evaluations will not be carried forward.

The following are examples for subjects who will be counted as non-responder:

- Concomitant anti-TNF- α treatment or other treatments with clinically relevant impact on HS;
- Antibiotic rescue therapy;
- Non-protocol specified lesion intervention, or higher than permitted frequency or number of pre-specified lesion interventions. Protocol-specified lesion interventions will *not* be counted as Non-responder.

Concomitant therapy that would qualify a subject as non-responder will be reviewed prior to database lock. More details will be provided in the Statistical Analysis Plan (SAP).

Missing Data Analysis: For missing data analysis, the following imputation rules will be applied to categorical and continuous efficacy variables, respectively:

- Categorical Efficacy Variables: NRI will be the primary approach for categorical variables. The NRI analysis will count subjects who have missing values at a specific visit as non-responders for that visit. LOCF will be the secondary approach for the missing data analysis.

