Continuous variables will be analyzed using a mixed effects model for repeated measures. This model will include treatment group, visit, treatment-by-visit interaction, and randomization strata (Hurley Stage II or Hurley Stage III, previous anti-TNF- α drug use or anti-TNF- α drug naïve, concomitant antibiotic therapy use or not) as factors, and baseline as covariate. Subjects will be considered as repeated measure units over visits. Testing p-values, point estimates and corresponding 95% confidence intervals will be estimated for the difference between the

avacopan group and the placebo control group across 12 weeks using linear contrast from the model.

For the analysis of subject's global assessment of skin pain (NRS30) up to Week 12, subjects who received analgesics or disallowed pain therapy will be counted as non-responder for categorical variables. For continuous variables, LOCF applies. Hereby, the last pain assessment is carried forward from the start day of the analgesics or day of the intervention until 14 days after the stop of analgesic use or day of the intervention. Concomitant medication for treatment of pain will be reviewed. Disallowed pain therapy will be determined by a blinded data review prior to database lock.

The test of 10 mg vs. 30 mg avacopan groups will be conducted at each timepoint for the endpoint of the proportion of subjects achieving HiSCR and the secondary endpoints. A detailed Type I management plan for the secondary endpoint testing will be provided in SAP.

8.8.4. Analysis of Secondary and Other Efficacy Endpoints in Period 2

The efficacy data for secondary and other endpoints by timepoint in Period 2 will be summarized using the mITT2 population. Analysis of other efficacy endpoints will be conducted from Day 1 to each timepoint.

For the analysis of time to loss of response (LOR), the treatment difference between the 10 mg and 30 mg avacopan groups will be analyzed using the stratified log-rank test with baseline randomization stratification factors as the stratification variables.

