For secondary efficacy endpoint testing, the avacopan 30 mg vs. placebo or the avacopan 10 mg vs. placebo will be tested separately with the $\alpha = 0.05$ level, provided that the corresponding primary endpoint testing of the same dose level is significant. As the two drug doses are two independent families, and the outcome of the study is to select one dose, not 2 doses. A fixed hierarchical testing sequence will be employed, as following:

H₂: Change from Baseline in total AN count at Week 12

H₃: NRS30 at Week 12

H₄: % subjects with baseline Hurley Stage II who achieved AN count of 0, 1, or 2 at Week 12

H₅: Reduction of IHS4 at Week 12

H₆: Change from Baseline in inflammatory nodule count at Week 12

H₇: Change from Baseline in abscess count at Week 12

H₈: Change from Baseline in draining fistula count at Week 12

H₉: Change from Baseline in Modified Sartorius score at Week 12

Comparisons involving other efficacy endpoints and time points are considered supportive or exploratory and will be made at α =0.050 level (two-sided). No multiplicity adjustment will be made for these comparisons.

J. Analysis Populations

Analysis populations will be defined for use with various analyses.

Intent-to-Treat Population

The Intent-to-Treat (ITT) Population will include all subjects who are randomized and have received at least one dose of study drug, and who are not from study Site 138. Subjects from Site 138 will be excluded from the ITT Population due to potential misconduct and non-compliance at site 138.

The ITT populations are defined for the two treatment periods as the following:

- The ITT1 Population in Period 1 is defined as all subjects who are randomized at baseline and have received at least one dose of study drug during Period 1.
- The ITT2 Population in Period 2 is defined as all subjects who have received at least one dose of study drug during Period 2.

Per Protocol Population

The per protocol (PP) population for period 1 will consist of ITT1 and do not have protocol deviations that could significantly affect the interpretation of the results for the primary endpoints. Subjects' inclusion/exclusion from the PP population will be determined and documented prior to the database lock and unblinding.

Per-Protocol Population in Period 1 (PP1) will include subjects in ITT1 who meet all the following criteria:

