2) Non-Responder Imputation for Any Add-on Antibiotics/Other Concomitant Medications Use

All subjects with any add-on antibiotics (any antibiotics other than the concomitant at Baseline) or with dose increase from baseline concomitant antibiotics prior to Week 12, regardless the reason for use; or other concomitant medications listed below will be imputed as non-responders:

- Add-on antibiotics
- Concomitant Anti-TNF-α treatment
- Concomitant other systemic treatment for HS. E.g., methotrexate, cyclosporine, retinoids, and fumaric acid esters, etc.

3) LOCF for HiSCR

Subgroup Analysis

Subgroup analyses will be performed for the primary efficacy endpoint in the ITT1 Population.

The subgroups are defined as follows:

- Randomization stratification variables
 - Hurley Stage (II, III)
 - Concomitant antibiotic therapy (Yes, No)
 - Anti-TNF-α treatment (Treatment naïve, Previous treatment)
- Sex (Male, Female)
- BMI category: Normal (< 25 kg/m²), Overweight (25 − < 30 kg/m²), obese (30 − < 40 kg/m²), Morbid obesity (≥ 40 kg/m²)
- Age at diagnosis of HS (< median, ≥ median)
- Age at study entry (<65 years vs. ≥ 65 years)
- Duration of HS (< median, ≥ median)
- Race (White vs. None-White)
- Baseline AN count (<5, 5-10, >10)
- Baseline inflammatory nodule count (< median, ≥ median)
- Baseline abscess count (< median, ≥ median)

- Baseline draining fistula count (< median, ≥ median)
- Baseline modified Sartorius score (< median, ≥ median)
- Previous systemic HS treatment (includes TNF inhibitor use but excludes antibiotic use)
- Geographic distribution (Northeastern Region, Southeastern Region, Western Region, Midwestern Region, and Southwestern Region)

These summaries will be based on imputed data (NRI for binary variables). If the sample becomes sparse in one of the subgroup strata, the subgroup variable will be collapsed or removed from the subgroup analysis.

Exploratory Analysis

The avacopan 10 mg vs. 30 mg groups will be tested for the primary efficacy endpoint if the primary efficacy endpoint tests of both avacopan 10 mg vs placebo and avacopan 30 mg groups vs placebo are statistically significant in the ITT1 Population.

E. Secondary and Other Efficacy Endpoints Analyses

The following missing data handling rules will apply:

Secondary/Other Efficacy Endpoints

- For binary efficacy variables, NRI imputation method will be used for missing data. For NRS30 in Period 1, multiple imputation method will be applied similarly as the primary endpoint.

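### The SAP confines the direct 10 mg vs 30 mg comparison in Period 1 to the primary endpoint, and to the case where both doses beat placebo, without listing this departure from Protocol 8.8.3

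*SAP*

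**What the plan says.** **Protocol 8.8.3** (secondary and other endpoints, Period 1): "The test of 10 mg vs. 30 mg avacopan groups will be conducted at each timepoint", for the HiSCR proportion and for the secondary endpoints. No condition is attached.

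**SAP VIII.D** (in its exploratory part): "The avacopan 10 mg vs. 30 mg groups will be tested for the primary efficacy endpoint if the primary efficacy endpoint tests of both" doses against placebo are significant in ITT1. No other timepoint or endpoint is mentioned.

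**SAP VIII.E, Period 1**: the secondary endpoints are tested as 30 mg against placebo and 10 mg against placebo. No contrast between the doses is named.

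**SAP VI.I**: each dose gets its own secondary-endpoint sequence at 0.05. One reason given is that "the outcome of the study is to select one dose, not 2 doses".

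**SAP I.A** says that the SAP's definitions and methods override the protocol's. **SAP X**, the table of changes from the protocol, has rows for multiplicity and for the ranked secondary endpoints. It has none for the new condition or for the dose contrasts that are no longer named.

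**The concern.** The 10 mg vs 30 mg test is headed exploratory and no later hypothesis in VI.I depends on it. Making it wait for two significant placebo comparisons therefore protects no confirmatory claim. What the condition does is remove a direct comparison whenever either dose misses.

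The awkward case is a split result. Suppose 30 mg reaches significance and 10 mg falls just short, or the reverse. Readers will be drawn to conclude that the doses differ, but a significant result next to a non-significant one is not evidence of that. The direct contrast with its interval is what would answer the question, and in that case the SAP plans neither.

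The question is a live one. Protocol 3.5 credits both doses with high receptor blockade (at least 90% for 10 mg, at least 95% for 30 mg) and includes 10 mg to explore how low an effective dose can be. The SAP also leans on dose selection to justify its multiplicity scheme while narrowing the comparison that would inform such a selection.

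**Working it through.** **1. Inputs.** From Protocol 8.3 (repeated in SAP IV.C): 130 subjects per group, two-sided 0.05, placebo HiSCR about 30%, and 50% for avacopan ("assuming an HiSCR at Week 12 of 50% in the avacopan group"). No separate rate is given for 10 mg, so it is an assumption below, varied from 50% down to 30%.

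**2. The plan's own figure.** The plan says that this size "provides approximately 90% power to detect a 20% superiority of avacopan" over placebo. Power = Φ[(d − 1.96·se0)/se1], with d = 0.20:
- se0 = √(2 × 0.40 × 0.60/130) = 0.0608
- se1 = √((0.30 × 0.70 + 0.50 × 0.50)/130) = 0.0595
- Power = Φ[(0.20 − 0.1191)/0.0595] = Φ(1.36) = 91.3%

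At 121 per group (7% attrition) it is 89.3%. The stated 90% reproduces, but it is for one dose against placebo.

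**3. How often the condition fails.** Simulation of 400,000 trials per row: three binomial arms of 130, unstratified pooled z-tests sharing one placebo arm, placebo 30%, 30 mg 50%.

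| Assumed 10 mg rate | Both doses significant | Comparison not made | Only 30 mg significant | Of those, direct test not significant |
|---|---|---|---|---|
| 50% | 85.2% | 14.8% | 6.2% | 82% |
| 45% | 67.6% | 32.4% | 23.7% | 66% |
| 40% | 38.7% | 61.3% | 52.5% | 44% |
| 35% | 13.7% | 86.3% | 77.6% | 21% |
| 30% | 2.5% | 97.5% | 88.7% | 6% |

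Column 3 is 100% minus column 2. At 121 per arm, the first three rows of column 3 become 17.4%, 34.8% and 63.5%. With the doses reversed (10 mg 50%, 30 mg 40%), both are significant in 38.8% of trials, and in 52.6% only 10 mg is nominally significant.

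**4. What a direct comparison could show.** At 40% vs 50% and 130 per arm:
- Power = Φ[(0.10 − 1.96 × 0.0617)/0.0614] = Φ(−0.34) = 37%; 80% power would need 388 per arm.
- 95% interval half-width = 1.96 × √((0.40 × 0.60 + 0.50 × 0.50)/130) = 1.96 × 0.0614 = 0.120, about ±12 points.

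The contrast is therefore useful as an estimate with an interval, not as a decisive test.

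**5. Whether another planned analysis fills the gap.** SAP VIII.E plans log-rank tests of time to loss of response in Period 2, comparing 30 mg with 10 mg without any condition. Loss of response is measured against each subject's own improvement by Week 12, so these tests concern durability, not the size of the Week 12 response. The Period 2 repeated-measures model compares each dose with the pooled placebo-to-avacopan group, not with the other dose.

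**The case against.** Several stronger readings are tempting, and the documents do not support them.

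- **That this is the plan's only direct dose comparison.** It is the only one in Period 1; the Period 2 log-rank tests are direct and unconditional.
- **That the comparison is withheld just where dose choice matters most.** The choice between doses is arguably most open when both beat placebo, and then the test is run. The gap is the split result.
- **That Period 1 would yield no dose information.** SAP VI.L tabulates 10 mg and 30 mg separately in every case, and VIII.D gives each dose an interval against placebo. The observed dose difference follows by subtraction; its interval does not.
- **That dose selection is a study objective, or that a dose would be picked by comparing p-values.** The objectives do not mention selection. It appears as a rationale for multiplicity, and no selection rule is stated anywhere.
- **That the SAP expressly cancels the secondary-endpoint dose contrasts.** It is silent on them and lists only placebo contrasts, so their status is unclear.

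Two further points against the concern have weight. The condition does reduce chance findings: with both doses at 50%, significant dose differences fall from 5.4% to 3.2% of trials. But this is an exploratory test, and the argument does not apply to an interval reported as estimation. Second, the documents' single avacopan rate, if applied to both doses, is the mildest scenario, with the comparison made in 85% of trials. The larger shares depend on an assumed lower 10 mg rate. The low power is also real, and it favours an interval over a test.

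**Conclusion.** The point holds as a narrow one. The protocol's unconditional dose comparison has become a conditional one on a single endpoint, the Period 1 secondary contrasts between doses are no longer named, and Section X records none of this. The condition protects no confirmatory conclusion and leaves a split result without a planned Week 12 dose contrast or interval.

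The comparison would be missing in about 15% of trials if 10 mg matches 30 mg at 50%, 32% if 10 mg is 45%, and 61% if it is 40%. These figures rest on 130 per arm, placebo 30%, unstratified tests and assumed 10 mg rates. The primary analysis and its error control are unaffected; this is a cheap improvement in what the trial reports, plus a record to correct.

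**What to change.** - **SAP VIII.D:** remove the condition that both doses be significant. Report the 30 mg minus 10 mg difference in Week 12 HiSCR with a stratified 95% interval, by the same stratified Newcombe method used against placebo, whatever the placebo comparisons show.
- **SAP VIII.E:** add the matching Week 12 dose contrast for each ranked secondary endpoint, from the repeated-measures model for the six continuous endpoints and as a stratified difference for the two binary ones.
- **Labelling:** describe all of these as exploratory estimation that uses no alpha. VI.I needs no dose-selection rule.
- **SAP X:** list whatever departure from Protocol 8.8.3 remains, for example if comparisons at other timepoints are not kept.

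The cost is some wording and a few extra contrasts. The drawback is wide intervals, about ±12 points for HiSCR, which must not be read as showing that the doses are equivalent.

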- ANTIB is the variable for concomitant antibiotic therapy with allowed antibiotics (0 for No; 1 for Yes)
- ANTITNF is the variable for anti-TNF drug use (Treatment naive vs. Previous treatment)
- BASE is the variable for the corresponding baseline value

CONFIDENTIAL

SUBJID is for subject

For the analysis of subject's global assessment of skin pain (NRS30) up to Week 12, subjects who received analysis (to be determined by classification prior to database lock), for skin pain, or have undergone intervention will be counted as non-responder for categorical variables, and have their last pain assessment before the start of the analysis or date of the incision and drainage (I&D) carried forward

for continuous variables, from the start day of the analgesics or day of the I&D until 14 days after the stop of analgesic use or day of the I&D.

LOCF and as observed analysis will be the sensitivity analyses for categorical variables and for continuous variables, respectively

Disallowed pain therapy will be determined by a blinded data review prior to database lock.

In addition, as a sensitivity analysis for Period 1, for selected secondary efficacy endpoints (continuous variables), an ANCOVA model with treatment, baseline value, Hurley Stage (Stage II vs. III), concomitant antibiotic therapy with allowed antibiotics (Yes vs. No) and anti-TNF drug use (Treatment naïve vs. Previous treatment) will be also applied based on OC; for selected secondary efficacy endpoints (binary variables), Multiple imputation (MI) method will be applied. The following are selected secondary efficacy endpoints:

- Reduction of IHS4 score relative to baseline over time (MMRM model, and ANCOVA model); Log ratio of IHS4 score to baseline over time (MMRM model).
- Proportion of subjects achieving at least 30% reduction and at least 1 unit reduction from Baseline in the subject's global assessment of skin pain (NRS30) in subjects with a Baseline NRS of at least 3, evaluated at each time point to Week 12 (NRI, and MI).
- Change from Baseline in the modified Sartorius score to quantify the severity change of HS (MMRM model, and ANCOVA model)
- The Short Form-36 version 2 (SF-36 v2) (MMRM model, and ANCOVA model)
- The EQ-5D-5L (EQ-5D-5L) (MMRM model, and ANCOVA model)
- The Hidradenitis Suppurativa Quality of Life (HiSQOL) Index (MMRM model, and ANCOVA model)
- the Dermatology Life Quality Index (DLQI) (MMRM model, and ANCOVA model)
- The Work Productivity and Activity Impairment Questionnaire: Specific Health Problem (WPAI:SHP), change from baseline to Week 12 (MMRM model, ANCOVA model)

For the other endpoints, only the primary analysis will be applied.

For the analysis of variables in Period 1, not by visit, such as: duration of flare, health-economic information on hospitalizations, emergency or urgent care visits,

and lesion interventions for HS, an analysis of covariance (ANCOVA) model with treatment, baseline value, Hurley Stage (Stage II vs. III), concomitant antibiotic therapy with allowed antibiotics (Yes vs. No), and anti-TNF drug use (Treatment naïve vs. Previous treatment) will be applied. Treatment comparisons between the avacopan group and the placebo control group will be presented.

2. Analysis of Secondary and Other Efficacy Endpoints in Period 2

The efficacy data for secondary and other endpoints by timepoint in Period 2 will be summarized using descriptive statistics in the ITT2 population.

For binary variables, Non-Responder Imputation will be used; for change from baseline variables, other than lesion counts endpoints, no missing data imputations will be performed.

For selected secondary efficacy endpoints specified above, a MMRM model including treatment group, visit, treatment-by-visit interaction, and randomization strata (Hurley Stage II or Hurley Stage III, previous anti-TNF-α drug use or anti-TNF-α drug naïve, concomitant antibiotic therapy use or not) as factors, and corresponding baseline as covariate will be applied in Period 2. Testing p-values, point estimates and corresponding 95% confidence intervals will be estimated for the difference the avacopan 30 mg vs. total placebo to avacopan group, and avacopan 10 mg vs. total placebo to avacopan group across visits in Period 2 using linear contrast from the model.

For the analysis of time to loss of response (LOR), the treatment difference between the avacopan 30 mg vs. placebo to avacopan 30 mg, avacopan 10 mg vs. placebo to avacopan 10 mg, avacopan 30 mg group vs. avacopan 10 mg group, and placebo to avacopan 30 mg vs. placebo to avacopan 10 mg will be analyzed using the stratified log-rank test with the baseline Hurley Stage (Stage II vs. III), concomitant antibiotic therapy with allowed antibiotics (Yes vs. No), and anti-TNF drug use (Treatment naïve vs. Previous treatment) as the stratification variables. Subjects without LOR or lost follow-up will be censored at the date of the last assessment of number of HS lesions. Kaplan-Meier curves will be provided by treatment group.

IX. Safety Analyses

Safety analyses will be performed in the Safety Analysis Set using the actual treatment group.

A. Adverse Events

All subjects will be assessed regularly for potential occurrence of adverse events (AEs) throughout the study until the subject is off study. The Medical Dictionary for Regulatory Activities (MedDRA; Version 21.1) will be used to code all adverse events to a System Organ Class (SOC) and Preferred Term (PT).

A treatment-emergent AE (TEAE) in Period 1 is defined as any AE that occurs after the first dose of study treatment in Period 1 and before the date of first dose of study treatment in Period 2.

A treatment-emergent AE (TEAE) in Period 2 is defined as any AE that occurs after the first dose of study treatment in Period 2.

A treatment-emergent AE (TEAE) for all avacopan, is defined as any AE that occurs after the first dose of avacopan treatment in study.

The incidence of TEAEs will be summarized and tabulated by treatment group and period.

The severity of each AE will be assessed as mild, moderate, severe, lifethreatening, fatal, or death. Several occurrences of the same AE in one subject will be counted once and the one with maximum severity will be counted.

The relationship of each AE to the blind study medication will be classified as probably not related or possibly related. Several occurrences of the same AE in one subject will be counted once and the one with the maximum relationship to blind study medication will be counted. If an AE is missing the relationship to blind study medication, the event will be assumed to be probably related for analysis and summarization.

Adverse Events of Special Interest (AESI) include infections, hepatic enzyme elevations, neutropenia and lymphopenia, hypersensitivity/angioedema, creatine phosphokinase elevation, malignancies, and HS Lesion interventions.

Infections: The subject incidence of serious infections, severe infections (i.e., Grade 3+), and infections leading to subject withdrawal from the study will be summarized by treatment group. Infections will be identified by selecting terms with the Adverse Event System Organ Class of 'Infections and Infestations'.

Hepatic transaminase elevations:

The following lab abnormalities will be included in this category:

- Grade 3 or greater increased ALT or AST (>5 times the upper limit of normal)
- Grade 2 or greater increased ALT or AST (>3 times the upper limit of normal) with elevation of bilirubin to >2 times the upper limit of normal or INR >1.5

Neutropenia, lymphopenia and leukopenia:

The following lab abnormalities will be included in this category:

Grade 3 or greater neutropenia (<1 x 109/L)

- Grade 4 lymphopenia (<0.2 x 109/L)
- Grade 3 or greater leukopenia (WBC count <2 x 109/L)

Hypersensitivity reactions: The subject incidence of adverse events associated with hypersensitivity/angioedema and urticaria will be summarized by treatment group. Terms will be based on the Standardized MedDRA Query for hypersensitivity.

Creatine Phosphokinase Elevation:

Grade 3 or greater CPK increase (>5 times the upper limit of normal)

Malignancies: Any malignancies will be reported as AEs.

HS Lesion Interventions: Lesion interventions due to HS will be recorded in CP.

The following summaries will be presented in tables:

- Overall summary of TEAEs
- TEAEs by SOC and PT. (The number and percentage of subjects with at least one TEAE, as classified by system organ class (SOC) and preferred term (PT), will be summarized by treatment received in the period of onset. For these summaries, subjects with multiple events will be counted only once per SOC and preferred term.)
- TEAEs by SOC, PT and maximum relationship to study drug
- TEAEs by SOC, PT and maximum Severity
- Serious TEAEs by SOC and PT
- TEAEs leading to withdrawal the study drug by SOC and PT
- TEAEs of special interest by SOC and PT
- TEAEs by PT in descending order
- SAEs by PT in descending order

The AE listings will be prepared, sorted chronologically within subjects for the following types of AEs. Each listing will include system organ class, preferred term, onset and end date, severity, relation to study drug, action taken, outcome, and SAE status.

- All AEs
- Serious AEs
- TEAEs leading to death
- TEAEs leading to withdrawal the study drug
- TEAEs of special interest

B. Clinical Laboratory Results

Laboratory test results include:

- Hematology: hemoglobin, hematocrit, RBC count, WBC count with differential, platelet count, mean cell hemoglobin, mean cell hemoglobin concentration, mean corpuscular volume.
- Serum Chemistry: liver panel (total bilirubin, lactate dehydrogenase, aspartate
 aminotransferase [AST], alanine aminotransferase [ALT]), renal panel (blood
 urea nitrogen, creatinine), creatine phosphokinase (CPK), albumin, sodium,
 potassium, magnesium, bicarbonate, chloride, calcium, inorganic phosphorus,
 glucose, total protein, alkaline phosphatase, total cholesterol, uric acid, serum
 amylase, and serum lipase.
- Urinalysis: nitrite, blood, and protein. If positive, microscopy will be performed;
- Virology (measured only at screening and may be measured at the local laboratory): hepatitis B surface antigen, hepatitis C antibodies, HIV 1 and 2 antibodies.
- TB screen: interferon γ release assay (IGRA).
- Pregnancy test: serum pregnancy test

All laboratory values will be converted to International System of Units (SI units). Lab results will be graded by the low/normal/high classifications based on normal ranges.

Laboratory data (actual values and change from baseline) will be summarized with the mean, standard deviation and median by treatment group and study visit. Laboratory data will be listed by treatment group, subject, and study visit. The CTCAE grades will be provided for selected Lab parameters. Abnormal laboratory values will be flagged.

The subject incidence of elevated laboratory values of ALT, AST, total bilirubin, alkaline phosphatase as assessed by the Central Laboratory, will be summarized by treatment group and Grade, as defined per Common Terminology Criteria for Adverse Events (CTCAE) Version 5. Shift from baseline to highest CTCAE grade during the study period will also be produced for these laboratory parameters based on the Central Laboratory measurements.

The same summary by treatment and CTCAE grade will be produced for subject incidence of elevated creatine phosphokinase (CPK), low neutrophils, low lymphocytes, low leukocytes, low hemoglobin, and low platelets. Shift from baseline to highest CTCAE grade during the study period will also be produced for these laboratory parameters. A by-subject listing including all data for these laboratory parameters including CTCAE grade for subjects with any abnormality will be provided

Urine and serum pregnancy test results for female only, HIV screening results, Hepatitis B/C screening results, and tuberculosis screening results will be listed.

C. Vital Signs

The following vital signs variables will be summarized: systolic blood pressure (mmHg), diastolic blood pressure (mmHg), temperature (°C) and heart rate (beats/min) and weight (kg). The following summaries will be provided:

- A summary of the absolute and change from Baseline value for each vital sign variable by treatment group, visit, and period.
- A summary of the number and percentage of subjects experiencing at least one Potentially Clinically Significant Vital Sign Findings by treatment group and visit.

Definitions of Potentially Clinically Significant Vital Sign Findings

Parameter (unit)	Category	Markedly Abnormal Values
Systolic	Low	≤ 90 mmHg or decrease ≥ 20 mmHg from
Blood	Value	Baseline
Pressure	High	≥180 mmHg or increase ≥ 20 mmHg from
(mmHg)	Value	Baseline
Diastolic	Low	≤ 50 mmHg or decrease ≥ 15 mmHg from
Blood	Value	Baseline
Pressure	High	≥105 mmHg or increase ≥ 15 mmHg from
(mmHg)	Value	Baseline
Heart Rate	Low	≤ 50 bpm or decrease ≥ 15 bpm from
(bpm)	Value	Baseline
1	High	≥ 120 bpm or increase ≥ 15 bpm from
	Value	Baseline

A by-subject listing of all vital signs data will be provided. This listing will be presented by treatment group with abnormal vital sign values flagged as "L" or "H" accordingly.

D. 12-Lead Electrocardiogram (ECG)

ECG results will be listed in the data listings. Abnormal ECG findings will be listed by treatment group and study visit, and clinical significance of abnormalities indicated.

E. Physical Examination

Physical examination will include assessment of appearance/mental status, head, eyes, ears, nose, throat, and the following body systems: dermatologic, cardiovascular, respiratory, gastrointestinal, musculoskeletal and neurologic.

A listing will be provided for physical examination findings (i.e., normal or abnormal and whether each abnormality was clinically significant) by treatment, visit, body system.

F. Pharmacokinetic Analysis

Sample Collections

PK blood sample will be collected prior to the morning dose on Day 1 and at 0.5, 1, 2, and 3 (+/- 5 minutes) hours (per protocol 19 October 2018 and amendment 2.0) or at 0.5, 1, 2, 3, and 6 (+/- 5 minutes) hours (per protocol 19 October 2018 and amendment 1.0) following dosing. Single PK samples will be collected predosing at the subsequent visits at Weeks 2, 4, 8, 12, 16, 20, 28, 36, and 44. The date and time of the PK sample collection will be recorded. The date and time of the last dose of study drug prior to the PK sample collection will also be recorded.

For plasma concentrations and PK parameters of avacopan (CCX168) or metabolite M1, descriptive statistics will include the number of values, arithmetic mean, standard deviation, and coefficient of variation (CV%), geometric mean (GM), CV% GM and 90% confidence intervals, minimum, median, and maximum.

Data Assembly

The concentration data of avacopan and metabolite M1 as reported by the bioanalytical laboratory will be used without rounding for all analysis.

Subjects with major protocol deviation such as PK deviation or compliance issues may be excluded from the PK analyses (i.e., descriptive statistics) upon agreement with the Sponsor on a case-by-case basis but all data will be listed. Values that are excluded from the analysis will be footnoted appropriately.

The following general rules will apply for handling missing data or concentration below the lower limit of quantification (BLQ):

- All BLQs will be set to "0" for Day 1 visit.
- If the BLQ occurs between 2 quantifiable drug concentrations within a full PK profile for Day 1 visit, the BLQ is excluded from all PK assessments.
- All BLQ will not be imputed for Post-Day 1 Visits and will be excluded from the descriptive summary.

- Missing pre-dose concentrations on Day 1 will be set as "0" and included in PK evaluation
- Missing post-dose values on Day 1 or missing trough values for post-Day 1 visits will not be imputed and will be excluded from PK evaluation
- Values that are excluded from the analysis will be documented appropriately.
- Pre-dose values on Day 1 that are greater than 5% of C_{max} will be documented. A sensitivity analysis (with inclusion and exclusion of the subjects with the pre-dose concentration >5% of C_{max}) will be presented and documented in the study report.

The sample time of the pre-dose samples on Day 1 will be uniformly considered as time "0".

For Day 1 visit, individual PK plots or individual PK parameters, since there is no collection window specified for post-dose PK sampling, will be based on actual times recorded. For concentration versus time descriptive statistical summaries and mean plot preparation, nominal time points will be used. If the difference of post-dose sampling time is > 5 minutes from the nominal sampling times for time points <2 hours or >5% for time points \ge 2 hours, the corresponding concentration data will be excluded from the concentration summary and mean plot preparation, but will still be used in the individual plots and the calculation of PK parameter.

For Day 1 visit, if the pre-dose PK sample is collected after dosing, the corresponding concentration will be treated as a post-dose value and will be used for individual plotting and PK parameter calculation.

Post-Day 1 avacopan and its metabolite M1 plasma concentration results will be used to calculate trough plasma concentrations (C_{min}) over the course of the clinical trial.

For post-Day 1 visits (i.e. Weeks 2, 4, 8, 12, 16, 20, 28, 36, and 44), the allowable time window for PK sampling is \pm 3 hours (i.e. 25% of dosing interval of 12 hours) for C_{min} . If the exact time (measured from dosing) is outside of the collection window, there is no dosing time, or there is a compliance issue, the corresponding concentration will be excluded from trough concentration versus time descriptive statistical summaries and median plot preparation, but will still be used in the individual plots.

Non-numerical readouts except BLQ [e.g., NA (not available) or NRE (not reliable)] will be set as missing and will not be included in the PK evaluation.

Pharmacokinetic Concentration

For subjects with serial samples collected on Day 1:

Individual plasma concentrations of avacopan and its metabolite M1 will be listed, plotted, and summarized descriptively and graphically by treatment group.

- Individual plasma concentrations of avacopan and its metabolite M1 will be plotted on a linear and semi-logarithmic scale against actual sampling time points;
- Concentration data will be summarized by treatment at each nominal time point descriptively;
- Mean (±SD) plasma concentrations of avacopan and its metabolite M1 will be plotted on a linear and semi-logarithmic scale against nominal time points by treatment

For subjects with pre-dose sample collected on Post-Day 1 visits:

- Individual plasma concentrations of avacopan and its metabolite M1 will be plotted by treatment on a linear scale against visits;
- Trough concentration data, within allowable time windows, will be summarized by treatment at each visit descriptively.
- In addition, median trough concentrations (C_{min}) of avacopan and its
 metabolite M1 will be plotted overlaid with the scatter plot of individual
 trough concentrations by treatment on a linear scale against visits.
 For subjects who received active treatment in Period 1, this plot will include
 visits in both Period 1 and Period 2.
- The average steady state trough concentration of avacopan or its metabolite M1
 for each individual subject will be calculated for a to-be-defined steady-state
 time period (each subject needs to have at least 3 time points in this steady state
 period for the calculation). The global average steady state trough concentration
 of avacopan or its metabolite M1 will be listed and summarized descriptively.
- For subjects who received placebo in Period 1 (Week 1 through Week 12), the Period 2 concentration data (Week 16 through Week 36) will be analyzed separately from the subjects who received active treatment in Period 1.

Pharmacokinetic Parameter

PK analysis will be performed in the PK population. The following parameters for avacopan (CCX168) or metabolite M1 will be determined, where possible:

- C_{max} Maximum plasma concentration
- T_{max} Time of maximum plasma concentration
- AUC_{0-3h} Area under the plasma concentration-time curve from Time 0 to Hour 3 on Day 1
- AUC_{0-6h} Area under the plasma concentration-time curve from Time 0 to Hour 6 on Day 1
- C_{min} Trough level plasma concentrations at post-Day 1 visits

PK parameter calculations will be based on continuous time points from Day 1 (including Time 0).

Plasma PK parameters will be calculated by standard non-compartmental analysis. The actual collection times will be used for PK parameter calculation. The linear trapezoidal rule method (equivalent to the Linear Trapezoidal Linear Interpolation in WinNonlin® Professional) will be used in the computation of AUCs.

